7.1. Analysis Sets

The number of subject in each analysis set described in [Section 5.1](#) is tabulated.

A by-subject listing of analysis sets is provided for the enrolled analysis set, and an administrative listing of randomization scheme and codes is provided for all randomization numbers and block numbers, even those not assigned to a subject. Refer to the Core SAP for listing contents.

7.2. Enrollment

Enrollment by country and site is tabulated for the enrolled analysis set. Refer to the Core SAP for more details.

7.3. Subject Disposition and Withdrawals

Subject disposition is based on the "Eligibility Criteria," "Informed Consent," and "Subject Disposition" CRFs, unless otherwise noted.

A by-subject listing of subject disposition will be provided for the enrolled analysis set based on the "Subject Disposition" and "Informed Consent" CRFs and includes the following: date informed consent was signed, protocol version, study completion status (yes, no, ongoing); reason for not completing the study, including specify text for "other" and AE preferred terms (PTs); study drug start date; and last contact date. This listing also identifies subjects who terminated the study prematurely due to COVID-19.

7.3.1. *Subject Disposition from Enrollment to Randomization*

Subject disposition from enrollment to randomization is tabulated for the enrolled analysis set as the number and percentage of subjects in the following categories:

- Randomized
- Not randomized
 - Reasons for discontinuation (i.e., not completing the study), including not reported. For subjects whose reason is screen failure due to inclusion/exclusion criteria, the reasons for screen failure are also included from the "Eligibility Criteria" CRF
- Not randomized and terminated the study prematurely due to COVID-19. This has the same subcategories as "Not randomized."

7.3.2. *Subject Disposition from Randomization to Treatment*

Subject disposition from randomization to treatment is tabulated for the randomized analysis set by as-randomized treatment group and overall as the number and percentage of subjects in the following categories:

- Treated with study drug (identified as those with non-missing study drug start date)
- Not treated with study drug (identified as those with missing study drug start date)
 - Reasons for discontinuation (i.e., not completing the study), including not reported
- Not treated with study drug and terminated the study prematurely due to COVID-19. This has the same subcategories as "Not treated with study drug."

This document is confidential.

7.3.3. *Subject Disposition from Treatment to End of Study/Follow-up*

Subject disposition from treatment to end of study is tabulated for the safety analysis set by as-treated treatment group and overall as the number and percentage of treated subjects in the following categories:

- Completed the study (identified as those with “yes” response to the question “Did the subject complete the study?”)
- Did not complete the study (identified as those with “no” response to the question “Did the subject complete the study?”)
 - Reasons for not completing the study, including not reported
- Terminated the study prematurely due to COVID-19. This has the same subcategories as “Did not complete the study.”

7.4. **Protocol Deviations**

A relevant protocol deviation is a deviation from the protocol which is programmed from the database and which could potentially affect the interpretability of the study results. This type of deviation includes but is not limited to:

- Eligibility
- Subject management

The frequency table of relevant protocol deviations displays the number and percentage of subjects in deviation categories and subcategories by deviation type (e.g., eligibility, subject management) for the full analysis set. Results are displayed for all deviations, even those with 0 counts, unless otherwise specified. See Section 6.2.4.1 of the Core SAP for further details.

A by-subject listing of relevant, programmable protocol deviations is provided for the enrolled analysis set. Relevant protocol deviations are outlined in [Section 16](#).

A by-subject listing of significant protocol deviations is provided for the enrolled analysis set. This includes visit, type, and description, which are used as additional sorting variables.

A Microsoft Excel file of protocol deviations is provided by the data management vendor from the clinical trial management system (CTMS). This file serves as the raw data source of protocol deviations, and classifies deviation severity as major, minor, or exclude. Significant protocol deviations are defined as those with major severity. A footnote describes the raw data source and how significant protocol deviations are identified, e.g., “Significant protocol deviations are those with major severity reported by the data management vendor in the clinical trial management system.”

7.5. **Demographic and Baseline Characteristics**

A summary of demographic and baseline characteristics will be presented by treatment group and overall using the safety analysis set. Descriptive statistics will be calculated for continuous variables (age, BMI, height, and weight) at baseline. Frequency counts and percentages will be tabulated for categorical variables (age category, gender, childbearing potential if female, ethnicity, race, country, BMI category).

Demographic and baseline characteristics will also be listed by subject for the enrolled analysis set. Weight, height, and BMI will be listed with vital signs as detailed in [Section 10.3](#).

7.6. **Alcohol Consumption and Smoking History**

Alcohol consumption and smoking history will be listed by subject for the enrolled analysis set.

This document is confidential.

7.7. Medical History and Concomitant Diseases

Medical history as recorded at baseline will be summarized by treatment group and overall for the safety analysis set using the number and percentages of subjects reporting each system organ class (SOC) and preferred term (PT). Medical history will be sorted by descending overall total by SOC and PT within each SOC using the Medical Dictionary for Regulatory Activities (MedDRA) coding dictionary version 24 or later in the summary table.

Medical history will be listed by subject for the enrolled analysis set.

7.8. Non-Study Medications

Non-study medications taken during the course of the study will be presented in tabular form for the safety analysis set using Anatomical Therapeutic Chemical (ATC) classification level 4 terms (ATC4) and preferred name via the World Health Organization (WHO) Drug Global B3 March 2021 or later for the following types:

- Prior medications (previous, current)
- Concomitant medications

The definitions of medication types are in Section 6.2.6.3 of the Core SAP. Medications are displayed in descending order of overall frequency within therapeutic class and preferred name. Imputed medication start and stop dates are used to assign non-study medication type (previous, current, concomitant, follow-up) to all non-study medications. Refer to the Core SAP for non-study medication start and stop date imputation. Subjects will be counted only once for each ATC4 term in the event that they have multiple records of the same ATC level in the database.

A by-subject listing of all non-study medications is provided for the enrolled analysis set. Refer to the Zavegeptan Core SAP for listing contents.

7.8.1. *Prior Medications*

Prior medications will be summarized descriptively by treatment group and overall for the safety analysis set in two tables: one for prior medications (including both previous and current) and one for current medications.

7.8.2. *Concomitant Medications*

Concomitant medications will be summarized descriptively by treatment group and overall for the safety analysis set.

7.9. Extent of Exposure

Study drug is zavegeptan 300 mg daily, i.e., six 25 mg softgel capsules twice daily, taken in the morning and the evening. Study drug is dispensed in a wallet-type blister pack with a unique wallet ID and 8 wallets are placed into a subject specific kit with a unique kit ID. Each wallet covers 4 days of morning dosing (6 capsules) and evening dosing (6 capsules) dosing, for a total of 48 capsules. Sites will record the kit and wallet IDs dispensed to each subject on the Drug Accountability CRF.

Subjects report study drug exposure in the eDiary, whereas sites report study drug accountability in the Drug Accountability CRF.

This document is confidential.

Study drug exposure is tabulated as continuous or categorical variables by treatment group and overall for the safety analysis set and includes the following parameters:

- Time from study drug start to last contact (days), derived as: last contact date – study drug start date + 1
- Time on study drug (days), derived as: study drug end date – study drug start date + 1
- Time on study drug categories (weeks): 1, 2, 3, 4, or > 4
- Cumulative study drug exposure (mg), derived by summing {number of capsules × 25} across records with complete study medication start dates
- Average study drug exposure (mg per day), derived as cumulative study drug exposure/time on study drug (days)
- Total study drug exposure (mg) summed across all subjects, derived by summing cumulative exposure across all subjects
- Total study drug exposure (patient-years), derived by summing (study drug end date – study drug start date + 1)/365.25 across all subjects.

Study drug accountability is tabulated by treatment group and overall for the safety analysis set that includes the number and percentage of subjects in the following category:

- Study drug taken but subject not randomized
- Kit dispensed and all 8 wallets returned
- Kit dispensed and all 8 wallets not returned
 - Reason for wallets not being returned
- Number of capsules returned
- Number and percentage of subjects who took > 12 capsules on any 1 day
- Any partial/missed doses
- Compliance < 80%, derived as: (number of capsules dispensed – number of capsules returned)/(number of capsules expected to be taken) × 100%
- No study drug taken for ≥ 3 days (not necessarily consecutive) in any 1 week
- Incorrect study drug taken: all the time, or at least once

Incorrect study drug at least once means subject is (1) randomized to placebo group but received >=1 dose of study drug from study drug kit/container or (2) randomized to study drug group but received >=1 dose of study drug from placebo kit/container.

Incorrect study drug all the time means subject received incorrect study drug at least once (as defined above) and never received any randomized study drug.

A by-subject listing of study drug accountability is provided for the safety analysis set. Additionally, a by-subject listing of study drug accountability for partial/missed doses is provided for the safety analysis set.

An administrative listing of IP batch numbers is provided for the safety analysis set. Refer to the Core SAP for listing contents.

This document is confidential.

8. Efficacy

Efficacy will be measured via spirometry and lung function assessments. These assessments will be performed after each study dose treatment at Visit 5, Visit 6, Visit 7, and Visit 8. Methacholine PC₂₀ and airway inflammation will be assessed before and after study dose treatment, and allergen-induced methacholine PC₂₀, allergen-induced bronchoconstriction, and allergen-induced airway inflammation will be assessed following allergen challenges. All efficacy assessments will be performed on the mITT analysis set.

The methacholine inhalation test will be performed at Visit 2, Visit 4, Visit 5, Visit 6, and Visit 8. This test will measure FEV₁ at 30 and 90 seconds after each inhalation and, if necessary, at 180 and 300 seconds and beyond until the lowest response is captured. The test is terminated when a fall in FEV₁ of at least 20% (lowest post diluent FEV₁ versus lowest post methacholine concentration FEV₁) occurs, and the methacholine PC₂₀ is calculated. The PC₂₀ assessment will be performed at the start of each treatment period, then 24 hours before and 24 hours following allergen challenge as a measure of AHR.

The allergen inhalation challenge will be performed at Visit 3 and Visit 7. At Visit 3, doubling concentrations of allergen will be given until a 20% decline in FEV₁ is measured 10 minutes post-allergen inhalation versus baseline FEV₁. The FEV₁ will then be measured at regular intervals: 10, 20, 30, 45, 60, 90, 120 minutes, and 3, 4, 5, 6, and 7 hours after allergen inhalation to confirm both $\geq 20\%$ fall in FEV₁ (EAR) and $\geq 15\%$ fall in FEV₁ (LAR). The same final 3 doses of allergen administered during the screening period are administered during the dosing period challenge. The EAR is taken to be the largest fall in FEV₁ within 2 hours after allergen inhalation and the LAR is taken to be the largest fall in FEV₁ between 3 and 7 hours after allergen inhalation. The concentration of allergen that resulted in a 20% decline in FEV₁ will be selected for the allergen challenges at Visit 7 and Visit 8.

Sputum induction will be performed at Visit 2, Visit 3, Visit 4, Visit 5, Visit 6, Visit 7, and Visit 8. It will be performed 24 hours before allergen challenges and at 7 and 24 hours after allergen challenges, at the start of each treatment period, again at 24 hours before allergen challenges, and at 7 and 24 hours after allergen challenges. **CCI**

Allergy skin testing will be performed at Visit 1 or Visit 2. It will determine the allergen that is given to each patient in the inhalation allergen challenge. If an allergen provokes an allergic reaction, a raised itchy bump (wheal) and redness (flare) develops. The size of the wheal will be measured and recorded with a ruler in millimeters in the horizontal and vertical directions, perpendicular to each other after approximately 15 minutes. The size of the wheal for each antigen will be recorded. A reaction greater than 2 x 2 mm will be regarded as positive, provided that the positive and negative controls are appropriately positive (histamine) and negative (diluent), respectively.

Allergy skin titration testing will be performed at Visit 1 and Visit 2. It will identify the lowest titration of allergen that causes a skin wheal at least 2 x 2 mm in size. The diameter of each wheal is measured in 2 perpendicular directions after 10 minutes. The average wheal diameter for each dilution in the horizontal and vertical directions is recorded. The weakest dilution of allergen that produces an average wheal of at least 2 x 2 mm is the "skin test endpoint." This measurement is used to calculate the starting allergen dose for inhalation.

This document is confidential.

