For all objectives, the population of interest is defined through appropriate inclusion/exclusion criteria to reflect the targeted patient population for approval.

Intercurrent Events

Intercurrent events are those that occur after treatment initiation and either preclude observation of the endpoint or affect its interpretation.

- For efficacy objectives, study drug discontinuation is handled with a “treatment policy strategy”, i.e., the occurrence of the intercurrent event is considered irrelevant, such that all observed values of the endpoint of interest are used regardless of study drug discontinuation. This strategy aligns with the assumption that zavegepant is expected to confer benefits to the subject after study drug discontinuation. Thus, premature study drug discontinuation is ignored for these efficacy endpoints.

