4.2. Secondary Endpoints

Table 2: Secondary Objective Estimands

1 Objective	To evaluate the allergen-induced EAR 0 to 2 hours after the administration of the allergen inhalation challenge between subjects treated with zavegepant and placebo.
Efficacy Endpoint	Maximum percentage decrease from baseline in FEV ₁ at any time between 0 and 2 hours post-allergen challenge in the mITT analysis set.

This document is confidential.

	Summary	Same as that of primary estimand, with respect to EAR.
	Intercurrent Events	Treatment policy strategy : All available assessments on the subject are used regardless of intercurrent events.
2	Objective	To evaluate the AHR measured at 24 hours post-allergen challenge between subjects treated with zavegeptan and placebo.
	Efficacy Endpoint	Shift from pre-allergen challenge (Visit 6) to post-allergen challenge (Visit 8) of PC ₂₀ in the mITT analysis set.
	Summary	Difference in shift from pre to post-allergen challenge between the zavegeptan and placebo groups using an ANCOVA model.
	Intercurrent Events	Treatment policy strategy : All available assessments on the subject are used regardless of intercurrent events.
3	Objective	To assess the safety and tolerability of oral zavegeptan.
	Endpoint	Various safety endpoints (i.e., adverse events, clinically significant laboratory abnormalities).
	Summary	Frequency by treatment group of safety endpoints for the safety analysis set.
	Intercurrent	Not applicable

This document is confidential.

5. Analysis Sets, Treatment Groups, and Subgroups

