5.1. Analysis Sets

Enrolled: The enrolled analysis set includes all subjects who sign the informed consent form (ICF) and are assigned a subject identification number by the IWRS.

Full: The full analysis set includes enrolled subjects who receive a randomization treatment assignment from the IWRS.

Safety: The safety analysis set includes subjects from the full analysis set who received at least 1 dose of study therapy. The safety analysis set will be used for all analyses of safety endpoints. Subjects will be analyzed according to the treatment actually received.

Modified Intent-to-Treat (mITT): The mITT analysis set includes safety subjects (received at least 1 dose of study therapy) that provided at least 1 non-missing post-baseline LAR assessment. Subjects will be analyzed according to randomized treatment assignment.

Follow-up: Safety subjects whose last contact date is in the follow-up analysis period. This analysis set is used to assess follow-up safety.

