8.2.1. Early Asthmatic Response

The maximum percentage decrease in FEV₁ between 0 and 2 hours at Visit 7 will be compared between zavegeptan and placebo using ANCOVA. The maximum percentage decrease is the difference between the baseline (pre-allergen challenge) FEV₁ at Visit 7 and the lowest FEV₁ between 0 and 2 hours at Visit 7 divided by the baseline value from Visit 7. An ANCOVA model based on the decrease in FEV₁ between 0 and 2 hours at Visit 7 with treatment as a factor and baseline FEV₁ at Visit 7 as a covariate will be fitted. The baseline value is the measurement prior to dosing at Visit 7. The point estimate and 95% CIs will be reported for the difference in AUCs comparing zavegeptan and placebo.

Additionally, as a supportive analysis for the EAR, the AUC for percent decrease in FEV₁ between 0 and 2 hours at Visit 7 will be compared between zavegeptan and placebo using ANCOVA. AUC will

This document is confidential.

be calculated as described in Section 8.1.1. An ANCOVA model based on the AUC for the percent decrease in FEV₁ between 0 and 2 hours at Visit 7 with treatment as a factor and baseline (pre-allergen challenge) FEV₁ at visit 7 as a covariate will be fitted. The baseline value is the pre-allergen challenge measurement at Visit 7. The point estimate and 95% CIs will be reported for the difference in AUCs comparing zavegepant and placebo.

The minimum absolute FEV₁ value in 0 to 2 hours and AUC of the absolute FEV₁ values in 0 to 2 hours at Visit 7 will also be analyzed. AUC will be calculated as described in Section 8.1.1. The minimum absolute FEV₁ will be the lowest value between hours 0 and 2 post-allergen challenge at Visit 7. Both endpoints will be compared between zavegepant and placebo using an ANCOVA model with treatment as a factor and baseline FEV₁ at Visit 7 as a covariate. The baseline value is the measurement prior to dosing at Visit 7. The point estimate and 95% CIs will be reported for the difference in minimum absolute FEV₁ or AUC comparing zavegepant and placebo.

8.2.2. *Methacholine PC₂₀*

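### The early response (EAR) and methacholine PC20 are analysed only in subjects with a post-baseline late response (LAR), a value that neither endpoint uses

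*SAP*

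**What the plan says.** SAP Section 8 (Efficacy) sets one population for everything: "All efficacy assessments will be performed on the mITT analysis set". SAP Section 5.1 defines modified intent-to-treat (mITT) as subjects with at least one dose "that provided at least 1 non-missing post-baseline LAR assessment". Protocol Section 15.2 has the same condition but does not assign the set to particular endpoints.

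SAP Section 8 defines the late response: "the LAR is taken to be the largest fall in FEV₁ between 3 and 7 hours after allergen inhalation".

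The secondary estimand table in SAP Section 4.2 repeats the restriction for both efficacy endpoints. EAR is the maximum fall "at any time between 0 and 2 hours post-allergen challenge in the mITT analysis set". The airway hyperresponsiveness row reads "Shift from pre-allergen challenge (Visit 6) to post-allergen challenge (Visit 8) of PC ₂₀ in the mITT analysis set". Both rows also state: "All available assessments on the subject are used regardless of intercurrent events". The opening of SAP Section 4 says that, for all objectives, "the population of interest is defined through appropriate inclusion/exclusion criteria".

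**The concern.** Membership of the analysis set depends on a measurement made after randomisation that belongs to a different endpoint. The EAR window closes at 120 minutes and the first LAR reading is at 3 hours. A subject whose spirometry stops in between has a complete EAR that the SAP discards. Likewise, a subject who was challenged at Visit 7 and has PC20 at Visits 6 and 8, but no 3 to 7 hour reading, loses a valid PC20 shift.

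Two things are at stake. The first is precision, in a trial planned at 24 subjects that SAP Section 2 says was terminated early for low enrollment. The second is bias in the EAR comparison, if the absence of later readings is related to the size of the early fall. The documents neither state nor exclude such a link.

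**Working it through.** **What each endpoint needs**

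| Item | Data used at Visits 6 to 8 | Covariate | SAP section |
|---|---|---|---|
| mITT membership | At least one LAR assessment, so a 3, 4, 5, 6 or 7 h FEV1 at Visit 7 | – | 5.1, 8 |
| EAR, maximum fall | Visit 7 pre-challenge FEV1 and "the lowest FEV₁ between 0 and 2 hours at Visit 7 divided by the baseline value from Visit 7" | Visit 7 baseline FEV1 | 8.2.1 |
| PC20 shift | Visit 8 minus Visit 6 (log scale) | Visit 4 minus Visit 2 shift | 8.2.2 |

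The schedule of assessments places allergen inhalation only at Visits 3 and 7, so a post-baseline LAR must come from Visit 7. No 3 to 7 hour value enters the EAR or PC20 outcome or covariate. SAP Section 6.3 uses observed data, so a missing LAR is not imputed. The Core SAP applies only where this SAP is silent or refers to it (SAP Section 2), and here this SAP is explicit. It gives no alternative set and no sensitivity analysis for these endpoints.

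**Precision, if loss is unrelated to outcome**

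Inputs: SD 9, 12 per arm, two-sided 5% (SAP Section 3.5). The SD is the planning value for LAR, borrowed here for EAR. No covariate adjustment is made.

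Half-width = t(0.975, n1+n2−2) × 9 × √(1/n1 + 1/n2)

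- 12 v 12: 2.074 × 9 × 0.4082 = 7.62. An observed difference of 11 then gives 11 ± 7.62 = (3.4, 18.6), which reproduces the plan's table.
- 11 v 12: 7.81 (7.813/7.620 = 1.025, or +2.5%)
- 10 v 12: 8.04 (8.038/7.620 = 1.055, or +5.5%)
- 6 v 6 (assumed achieved size): 11.58
- 5 v 6: 12.33 (12.328/11.578 = 1.065, or +6.5%)

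**Bias in EAR, if loss follows a large early fall**

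This is an illustration under assumptions that are not in the documents: normal EAR with mean 30 on placebo and 19 on active (true difference 11), SD 9, and every subject with a fall above a cut-off c losing all later readings.

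Mean of those kept = μ − 9 × φ(z)/Φ(z), with z = (c − μ)/9. Proportion lost = 1 − Φ(z). Differences are taken before rounding.

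| c | Placebo mean kept | Active mean kept | Difference | Lost, placebo | Lost, active |
|---|---|---|---|---|---|
| 45 | 29.06 | 18.94 | 10.1 | 4.8% (0.6 of 12) | 0.2% |
| 40 | 27.77 | 18.76 | 9.0 | 13.3% (1.6 of 12) | 1.0% |
| 35 | 25.67 | 18.23 | 7.4 | 28.9% (3.5 of 12) | 3.8% |

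The last row is extreme. No PC20 bias figure can be given, because the documents supply no PC20 variance.

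**The case against.** The trigger is narrow. One reading at any of five time points appears to qualify a subject, spirometry at Visit 7 is scheduled to 7 hours with sputum induction then, and everyone in Part 2 has already shown a late response at screening. The same final three allergen doses are repeated at Visit 7. The PC20 route is narrower still, because the subject must return about 24 hours later without any late reading. All of this stands, and it is why the point is minor.

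The statements in SAP Section 4 can also be reconciled. An eligibility-based target population can coexist with a narrower analysis set, and the promise to use all available assessments can be read as covering subjects within the named set. That reading is fair. It removes the charge of contradiction, but the exclusion remains.

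The bias figures rest on assumed means and a hard cut-off, and the documents contain no rule that stops spirometry after a large early fall. They show direction and scale only.

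Endpoint-specific sets also condition on post-randomisation data, and a single 0 to 2 hour reading could understate a maximum fall. Both are true. However, such sets condition only on what the endpoint itself requires, and the present rule already accepts a single reading for LAR.

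Finally, a common set keeps all endpoints on the same subjects, which is defensible in a small Phase 1b trial. That benefit does not require discarding valid data from the main EAR and PC20 analyses.

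**Conclusion.** The concern holds, at minor severity. As written, the SAP drops valid EAR and PC20 data from any treated subject who has no 3 to 7 hour FEV1 at Visit 7, and nothing else in the two documents restores them. Only the secondary EAR and PC20 analyses and the supportive EAR analyses are affected.

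The size depends on how many subjects lack LAR, which the documents do not say; if none do, the effect is zero. Each of the first two subjects lost from one arm costs roughly 2.5% to 3% in CI width at the planned size, and one loss costs 6.5% at an assumed 6 v 6. Bias arises only if missing late readings are related to the outcome, and its amount cannot be estimated from the documents.

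**What to change.** In SAP Sections 4.2, 5.1 and 8, define the set by endpoint among treated subjects, analysed as randomised:

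- **EAR endpoints:** a pre-challenge FEV1 and at least one 0 to 2 hour post-challenge FEV1 at Visit 7.
- **PC20 shift:** PC20 at Visits 6 and 8, and an allergen challenge given at Visit 7, so that the shift is allergen-induced.
- **LAR endpoints:** keep the present LAR condition, for these only.

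Report the number in each set by arm. The cost is SAP wording and one population flag per endpoint, with no new data. The downside is that N may differ slightly between endpoints.
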